8.0 Study Design

8.1 * Study design (Help Text updated 9/13):

The goal of this study is to understand how simultaneous PET/MR acquisition can provide novel qualitative and quantitative information to guide clinical intervention and predict prognosis of patients with risk factors for the development of coronary artery disease, or with diagnosis of cardiovascular ischemic or inflammatory disorders.

Patients required to have a clinical cardiac FDG PET or PET/CT imaging study as part of standard of care, to detect myocardial viability or a cardiac inflammatory process will be enrolled in the study. After the initial acquisition of the clinical study patients will be immediately imaged in the PET/MRI system, with no additional administration of any radiopharmaceutical. The main purpose of the study would then be to compare the information provided from the clinical PET/CT with the one from the simultaneous cardiac PET/MRI.

8.2 If this is a clinical trial, check the applicable phase(s) (Help Text updated 9/13):

- Phase I
- Phase II
- Phase III
- Phase IV

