9.0 Scientific Considerations

9.1 Hypothesis (Help Text updated 9/13):

This study has a hypothesis:

Yes No

If yes, state the hypothesis or hypotheses:

We hypothesize that simultaneous acquisition of cardiac PET/MRI can provide some other benefits in comparison to stand alone scanners.

- In a hybrid system, real-time MR-based motion detection and correction could be applied since cardiac and respiratory gating can be image-based without external sensors. This could allow partial-volume correction and event-based correction of patient motion during the PET acquisition.
- Combined metabolic information provided by FDG and structural information offered by MRI can help to better define the extent, location and significance of infarcted myocardium or viable tissue, with special significance for non-transmural or transmural lesions.
- The lack of exposure to ionizing radiation and iodinated contrast agents makes hybrid PET/MRI attractive when compared with PET/CT.
- Both cardiac MRI and PET examinations can be rather time consuming. Thus, improvements in patient compliance as a result of reduced scan time could be significant, particularly in patients with dyspnea due to heart failure who have difficulty holding their breath during MRI acquisitions.
- Increased patient throughput based on reduced scan times is also likely to be cost-effective.

9.2 * List the specific aims:

- To compare regional myocardial uptake of FDG on images obtained on a standard PET camera with the new PET/MR camera, in patients with and without overt diagnosis of ischemic coronary artery disease.
- To compare viability maps obtained with cardiac MR images and FDG-PET for delineation of myocardial infarct core and border zone, in patients with coronary artery disease.
- To correlate MRI myocardial strain with relative myocardial FDG uptake in patients with a previous myocardial infarction, referred for a clinical myocardial viability study.
- To interrogate if simultaneous acquisition of cardiac PET and viability cardiac MR differ from acquisitions obtained independently, with special focus on attenuation correction methods.
- To combine MRI scar map with FDG-PET uptake in patients with cardiac sarcoidosis and myocarditis.
- To evaluate cardiac strain and myocardial scar burden in obese patients with and without diabetes.

9.3 Statistical analysis:

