To perform a combined analysis of sequential MRI and PET studies, images must be aligned accurately in the spatial domain. However, a particular challenge in cardiac studies is that the three spatial dimensions must be supplemented with a time dimension in order to correct for continuous motion during respiratory and cardiac cycles. Cardiac gating is routine in MRI and also possible in PET. Moreover, the integration of respiratory triggering is achieved using "navigators" (MRI) or list-mode acquisitions (PET). However, variable acquisition times between PET and MRI cause additional problems for exact timing of events. MRI scans are typically performed within few seconds during breath-holds while PET scans have a

minimum duration of 5 min. However, spatial co-registration is rarely addressed in studies using separate, sequential MRI and PET scans. Misalignment is mostly caused by significant patient motion, respiration, and cardiac contraction. The first two are very challenging, as they are involuntary and can produce irregular patterns. In their review, Mäkelä et al. summarized the co-registration accuracy for intra- and intermodal cardiac applications. For alignment of repeated MRI acquisitions accuracies of 1.5–3.0 mm were reported. Co-registration

accuracy of repeated PET studies was on the order of 1.0– 2.5 mm. Finally, alignment of gated PET with gated MRI images showed an accuracy of 2.0 ± 1.6 mm. In another study a misalignment of 2.8 ± 0.5 mm was calculated using

thorax and lung surfaces. Co-registration of any data not acquired simultaneously is therefore a major problem in inter- and intra-modal examinations.

Assessment of heart failure

Ventricular function

Determination of LV function in gated PET studies is based on the use of partial volume effects. As the effective spatial resolution in clinical cardiac PET scans is approximately 6– 10 mm FWHM (full-width at half-maximum), changes in

wall thickness can be estimated in terms of changes in regional count rates during cardiac contraction.

Using algorithm-dependent assumptions, such as homogeneous

tracer distribution over the myocardial wall, geometrical models can be used to estimate endo- and epicardial borders. This approach has been extensively implemented and validated in SPECT imaging and has also been

used in comparative MRI and PET studies. However, while being technically feasible, the accuracy of the assessment of global and regional LV function by PET

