11.0 Sample Size and Eligibility

11.1 Number of subjects that will be enrolled at UCSF and affiliated institutions:

60

11.2 Total number of subjects that will be enrolled at all sites (Help Text updated 9/13):

60

11.3 Estimated number of people that you will need to consent and screen here (but not necessarily enroll) to get the needed subjects:

120

11.4 Explain how and why the number of subjects was chosen (Help Text updated 9/13):

This is a pilot study and we anticipate a number of 50 patients to obtain data to generate a formal sample size calculation for a larger trial.

11.5 * Eligible age range(s):

- 0-6 years
- 7-12 years
- 13-17 years
- 18+ years

11.6 Inclusion criteria:

Subjects with ischemic and non-ischemic cardiac disease referred for cardiac PET for viability imaging.

11.7 Exclusion criteria:

Contraindications for MRI, including cardiac pacemaker, claustrophobia, retained metallic foreign body, cochlear implant, Aneurysm clip in the brain, pregnancy and eGFR less than 45%.

11.8 There are inclusion or exclusion criteria based on gender, race or ethnicity:

Yes No

If **yes**, please explain the nature and rationale for the restrictions:

12.0 Drugs and Devices**12.1 * Investigational drugs or biologics will be used OR approved drugs or biologics will be studied under this application:**

Yes No

12.2 * Investigational medical devices or in vitro diagnostics will be used OR approved medical devices or in vitro diagnostics will be studied under this application:

Yes No

12.3 * A Non-Significant Risk (NSR) determination is being requested for an investigational device:

Yes No

12.4 Verification of IND/IDE numbers: If the sponsor's protocol does not list the IND/IDE number, you must submit documentation from the sponsor or FDA identifying the IND/IDE number for this study. Attach this documentation in the Other Study Documents section of the Initial Review Submission Packet.

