17.0 Procedures

17.1 * Procedures/Methods [Help Text updated 9/13] For clinical research list all study procedures, test and treatments required for this study, including when and how often they will be performed. If there are no clinical procedures, describe the Methods:

The subjects will undergo PET/MR for study purposes after they have finished their clinically indicated PET/CT, with no additional venipuncture to the patients.

We propose to use 5D MR imaging (3D in space, in time through the cardiac cycle, and in time through the respiratory cycle) to provide improved information on the location of the signal source during PET acquisition.

Dynamic and static PET data will be acquired in list mode and retrospectively rebinned according to predicted location from MR data.

Accelerated MR methods (including compressed sensing) will be used to give rapid assessment of volumes over time.

Additional MR imaging sequences will include strain mapping and VEC-MRI for flow imaging. In addition gadolinium delayed enhancement will be obtained for myocardial tissue characterization with MRI.

If you have a procedure table, attach it to the submission with your other study documents.

17.2 Interviews, questionnaires, and/or surveys will be administered or focus groups will be conducted:

Yes No

List any standard instruments used for this study:

Attach any non-standard instruments at the end of the application.

17.3 Conduct of study procedures or tests off-site by non-UCSF personnel:

Yes No

If yes, explain:

17.4 Sharing of experimental research test results with subjects or their care providers:

Yes No

If yes, explain:

17.5 * Specimen collection for future research and/or specimen repository/bank administration:

Yes No

17.6 Time commitment (per visit and in total):

1 hour in the scanner.

17.7 Locations:

The cardiac MRI will take place at the China Basin radiology.

17.8 Describe the resources in place to conduct this study in a way that assures protection of the rights and welfare of participants:

1. The research team will make several efforts to keep the PHI under extreme security, including the use of a coded database, password protected computers and locked cabinets, which will all be kept inside a locked office at the Parnassus campus.
2. Patients are screened for prior claustrophobic symptoms using a screening form. Earplugs are provided to all patients in order to minimize the discomfort related to the loud noise.

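### Aim 4 compares simultaneous with independent acquisition, but no independent viability MR is planned, and the PET contrast cannot isolate simultaneity

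*Combined protocol and SAP*

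**What the plan says.** The fourth bullet of section 9.2, called Aim 4 here, reads: "To interrogate if simultaneous acquisition of cardiac PET and viability cardiac MR differ from acquisitions obtained independently". The sentence goes on to give attenuation correction as its special focus. It names two modalities, PET and viability MR, and sets their simultaneous acquisition against independent acquisition.

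The imaging is described in three places.

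- Section 8.1 gives the main purpose: to "compare the information provided from the clinical PET/CT with the one from the simultaneous cardiac PET/MRI". It also fixes order and tracer: "After the initial acquisition of the clinical study patients will be immediately imaged in the PET/MRI system, with no additional administration of any radiopharmaceutical".
- Section 17.1 repeats the sequence: "The subjects will undergo PET/MR for study purposes after they have finished their clinically indicated PET/CT". Strain mapping, flow imaging and gadolinium delayed enhancement are listed as MR sequences of that session. PET is to be stored in list mode and rebinned using MR-derived position. Section 17.6 gives a time commitment of 1 hour in the scanner.
- Section 11.6 sets entry: "Subjects with ischemic and non-ischemic cardiac disease referred for cardiac PET for viability imaging". No prior or concurrent MR is asked for. Section 18.2 names only FDG PET-CT as the care a non-participant would receive.

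Section 9.3 plans a correlation coefficient and Bland-Altman plots for linear variables from PET and cardiac MRI. It describes no analysis of simultaneous against independent acquisition.

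**The concern.** A comparison needs data on both sides. Aim 4 asks whether viability MR and PET differ when acquired together rather than separately, yet the only MR in the study is the one acquired with PET. For MR there is nothing to compare it with.

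For PET there is a second scan, but it differs from the PET/MR scan in several respects besides simultaneity. The protocol's own case for simultaneity is strong: section 10.2 says "Co-registration of any data not acquired simultaneously is therefore a major problem in inter- and intra-modal examinations". With no analysis specified for Aim 4, a difference between PET/CT and PET/MR could be reported as an effect of simultaneous acquisition when the design cannot attribute it. Because section 11.4 says the pilot is to inform a larger trial, that misattribution could be carried forward.

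**Working it through.** The plan gives no figure for this aim, so there is none to reproduce. The check is a count of acquisitions per subject on each side of the contrast.

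| Modality in Aim 4 | Obtained independently | Obtained simultaneously | Pairs per subject |
|---|---|---|---|
| PET | 1 (clinical PET or PET/CT; 8.1, 17.1) | 1 (PET/MR; 8.1, 17.1) | 1 |
| Viability MR | 0 (none in 11.6, 17.1 or 18.2) | 1 (delayed enhancement; 17.1) | 0 |

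**MR half.** Planned pairs = subjects × pairs per subject: 50 × 0 = 0 with the number in section 11.4, and 60 × 0 = 0 with the number in sections 11.1 and 11.2. Neither a bias nor limits of agreement can be estimated. Section 17.7 says where the cardiac MRI takes place; it does not describe a second MR. Section 17.1 invites an attached procedure table, which is not among the documents, but nothing in the text suggests that one would add a stand-alone MR.

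**PET half.** Between the clinical scan and the PET/MR scan these change together:

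1. the camera (Aim 1 in section 9.2 itself describes the contrast as one between cameras);
2. the attenuation correction, CT-based against MR-based (inferred from the scanner types);
3. the time since tracer administration, because one administration serves both scans (8.1);
4. the order, because the clinical scan always comes first (8.1, 17.1);
5. simultaneity with MR.

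Each subject yields one paired difference, and all five factors change in the same direction in every subject. The sum of their effects can be estimated, but no single effect can be separated from it. More subjects would narrow the interval around the sum and leave attribution where it was.

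**Precision if some subjects had a stand-alone MR.** The 95% half-width for a Bland-Altman limit, in units of the SD of paired differences, is t(0.975, n−1) × √(1/n + 1.96²/(2(n−1))).

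- n = 10: 2.262 × √(0.1000 + 0.2134) = 1.27 SD
- n = 20: 2.093 × √(0.0500 + 0.1011) = 0.81 SD
- n = 50: 2.010 × √(0.0200 + 0.0392) = 0.49 SD
- n = 60: 2.001 × √(0.0167 + 0.0326) = 0.44 SD

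The documents give no SD and no count of subjects with an earlier clinical MR, so the values of n are assumptions. With 10 to 20 such subjects a limit of agreement would be known only to within about 0.8 to 1.3 SD, which supports description and little more.

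**The case against.** The strongest reply is that Aim 4 declares a special focus on attenuation correction. That is a PET question, and PET has an independent comparator in the clinical scan. The study is also a pilot, Aim 4 is one of six aims, and the main purpose in section 8.1 does not need a stand-alone MR. All of this stands. It limits the point to the MR half and to the attribution of a PET difference. It does not remove viability MR from the aim's wording, and pilot status excuses imprecision rather than a missing comparator.

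A reader might infer more than the documents support, in four ways.

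- **That Aim 4 is wholly untestable.** It is not: the PET scans can inform its attenuation-correction focus.
- **That the PET contrast tests the camera.** It does not isolate the camera either, since the other four factors move with it.
- **That the study cannot address its hypothesis at all.** Section 9.1 lists five benefits, including less radiation and iodinated contrast, shorter scans and higher throughput. The absence of a stand-alone MR does not settle those, and motion correction has an acquisition plan in section 17.1.
- **That registering the clinical PET to the study MR, and comparing this with the PET/MR pairing, would isolate simultaneity.** Holding the MR fixed does not hold the PET fixed: scanner, timing and order still differ. Nor does the 2.0 ± 1.6 mm gated PET-to-MRI alignment quoted in section 10.2 give the size of the effect. Simultaneous alignment is not known to be perfect, since the same section contrasts breath-hold MRI of a few seconds with PET of at least 5 minutes and puts PET resolution at about 6–10 mm.

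**Conclusion.** The point holds in this limited form. The viability-MR half of Aim 4 has zero planned comparison pairs at any sample size and cannot be answered as designed. The PET half can be estimated as an overall difference between two imaging systems, but that difference cannot be attributed to simultaneous acquisition.

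The first conclusion rests on the text naming every scheduled scan. The second rests on the fixed order and single tracer administration, which are stated, and on the difference in attenuation method, which is inferred. Attribution would still fail without that inference, because camera, timing and order differ in any case. The size of any simultaneity effect is unknown, and the documents give nothing from which to derive it.

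**What to change.** Three changes to sections 9.2 and 9.3:

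1. Delete independently acquired viability MR from Aim 4. Alternatively, limit it to a descriptive analysis of subjects who already have a recent clinical stand-alone cardiac MR, with the permitted interval between scans stated in advance and the number of such subjects reported.
2. Describe the PET/CT versus PET/MR contrast as overall between-system agreement in regional FDG uptake, and state that it does not estimate an effect of simultaneity.
3. For motion and attenuation correction, reconstruct the same PET/MR list-mode data in more than one way: with and without MR-based motion correction and, where a clinical CT exists and registers adequately, with MR-based and CT-based attenuation maps. Report the paired within-subject differences in regional uptake. Because the emission data are the same in each pair, camera, tracer time and order are held constant. Section 8.1 allows a clinical PET without CT, so the second comparison may cover only some subjects, and any residual CT misregistration will be part of its result.

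No new scan, tracer or patient is needed. The costs are extra reconstruction work, retention of the list-mode data until it is done (section 24.6 has the data destroyed when the study ends), a narrower Aim 4, and an MR comparison that is either dropped or rests on a small subset.

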Correlation coefficient and Bland Altman plots will be applied to evaluate the agreement between linear variables obtained from PET and cardiac MRI.

9.4 If this study has undergone scientific or scholarly review, please indicate which entity performed the review:

Cancer Center Protocol Review Committee (PRC) (Full approval is required prior to final CHR approval for cancer-related protocols.)

CTSI Clinical Research Center (CRC) advisory committee

Departmental scientific review

Other:

Specify Other:

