is limited by the low resolution of the PET compared to that of MRI. Here, MRI is clearly the modality-of-choice to quantitate cardiac function, such as volumes, mass, ejection fraction and regional wall thickening. Determination of LV function is essential for the diagnosis of heart failure and its prognostic value is well established. Therefore, its combination with any other imaging parameter is likely to provide incremental information.

Myocardial viability

Ischemic myocardium that is dysfunctional but viable has the potential for recovery of contractile function after revascularization. Evaluation of myocardial glucose utilization with 18F -FDG PET is considered as the most reliable tool to assess myocardial viability. Its quantitative nature allows assessment of the amount of viable tissue as a continuum from fully viable, through partially viable in the

areas of non-transmural infarction, to non-viable scar. Contrast-enhanced MRI appears to be a promising alternative capable of visualizing transmural distribution of viable and infarcted myocardium with excellent spatial resolution. Contrast-enhanced MRI of myocardial infarction is based on the delayed-enhancement technique using inversion-recovery prepared T1-weighted gradient-echo pulse

sequences after intravenous administration of Gd-DTPA. Infarcted myocardium appears enhanced relative to normal myocardium when imaged with a delay (typically 5–20 min) after intravenous injection of the contrast agent due to

different wash-out kinetics. A comparison of delayed-enhancement MRI with 18F FDG PET and 13NH_3 in 31 patients with ischemic heart failure revealed that the location and extent of infarct scarring as delineated by delayed enhancement correlated very well with the non-viable segments from PET. The main source of difference between the methods was related to the presence of non-transmural enhancement in regions that were viable on PET. This can be explained by the higher spatial resolution of MRI compared with nuclear imaging methods that makes delayed-enhancement suitable for the detection of small areas of subendocardial infarcts. An improved contractile performance after intervention is commonly considered as the gold standard for assessing myocardial viability,

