although benefits of revascularization do not appear to be limited to improved function. In an initial study by Kim et al. in 41 patients with chronic ischaemic heart disease, dysfunctional segments with less than 25% of delayed enhancement were likely to recover after complete revascularization. In contrast, segments with more than 50% of delayed enhancement had a low probability ($<10\%$) of functional improvement. Comparable positive predictive values (73%) for functional recovery 6 months after revascularization were found for the lack of delayed enhancement (cut-off value less than 50% transmural scar) and the presence of preserved 18F -FDG uptake (cut-off value more than 50% of normal myocardium) as assessed by PET as the reference method to detect viable vs. nonviable myocardium. A recent meta-analysis of diagnostic studies indicated

that 18F -FDG PET has a higher sensitivity than delayed enhancement MRI (92% vs. 84%) in predicting functional recovery upon revascularization, while specificities were comparable (63%). The relatively low specificity of the techniques indicates that a substantial percentage of segments that are classified as viable by the imaging

techniques do not improve after revascularization. Although there are limited data on their combined use, adjunctive PET and MRI markers of viability, such as reduced diastolic wall thickness, lack of contractile response to inotropic stimulation with a low dose of dobutamine, preserved epicardial rim of viable myocardium, and preserved perfusion have been proposed to help refine the classification of dysfunctional segments as clinically viable or non-viable.

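### Section 9.3 offers a correlation coefficient as evidence of agreement, does not clearly name the PET/MR versus PET/CT comparison, and gives no unit of analysis for regional FDG uptake

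*Combined protocol and SAP*

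**What the plan says.** Section 9.3 of the combined protocol and SAP consists of one sentence: "Correlation coefficient and Bland Altman plots will be applied to evaluate the agreement between linear variables obtained from PET and cardiac MRI". It gives the two methods equal standing. It does not say which variables are meant, whether the patient or the region is the unit, or how repeated regions are handled.

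Section 8.1 gives the main purpose: to "compare the information provided from the clinical PET/CT with the one from the simultaneous cardiac PET/MRI". The first aim in section 9.2 (Aim 1, by order of listing) is "To compare regional myocardial uptake of FDG on images obtained on a standard PET camera with the new PET/MR camera". The third (Aim 3) is a different kind of question: "To correlate MRI myocardial strain with relative myocardial FDG uptake in patients with a previous myocardial infarction". The fourth (Aim 4) asks whether simultaneous and independent acquisitions differ, "with special focus on attenuation correction methods".

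Section 10.2 describes cited work by segment ("correlated very well with the non-viable segments from PET") and gives an FDG viability threshold on a relative scale ("cut-off value more than 50% of normal myocardium"). Neither is tied to this study's own analysis. No number of regions appears in the sample size section (11) or the procedures (17.1). Section 11.4 justifies about 50 patients by the need for data to size a larger trial; section 11.1 enters 60.

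**The concern.** There are three linked gaps.

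- **Correlation as agreement.** If one camera reads uniformly low, or low by a fixed percentage, r hardly moves. A study meant to validate a new system needs to detect exactly that. Attenuation correction, which Aim 4 singles out, is one route by which such a difference could arise. The Bland-Altman plot would show it, but the plan does not say that the conclusion rests on the plot.
- **Comparison not clearly named.** Section 9.3 speaks of PET against cardiac MRI. Aim 1 compares FDG PET on one camera with FDG PET on another.
- **No unit of analysis.** Regional uptake naturally gives several correlated values per patient. If these were treated as independent, any interval for the bias would be too narrow. A single pooled SD would also not separate between-patient from within-patient variance. A larger trial using several regions per patient would need that split for its sample size.

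**Working it through.** The plan has no figure to reproduce: it states no SD, agreement limit, region count or within-patient correlation. Every input below is an assumption, except the 60 patients of section 11.1.

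**1. What r misses (un-normalised uptake).** Let X have mean 8 and SD 3, and Y = 0.8X + noise with SD 0.3.
- SD of Y = √(2.4² + 0.3²) = √5.85 = 2.419, so r = 2.4/2.419 = 0.992.
- Bias = 0.8 × 8 − 8 = −1.60.
- SD of differences = √(0.2² × 9 + 0.09) = √0.45 = 0.671, so the limits are −1.60 ± 1.96 × 0.671 = −2.91 to −0.29.

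The plot shows the bias and r does not. Fixed limits also describe a proportional difference poorly. The slope of difference on mean is −1.575/7.3125 = −0.215 and the residual SD is 0.333. The limits are then about −1.5 to −0.2 at a mean uptake of 3.6, and −3.0 to −1.7 at 10.8. Hence the need for a proportional-bias check.

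**2. Pooling regions as independent (closed form).** With m regions per patient and intraclass correlation ICC of the differences:
- DEFF = 1 + (m − 1) × ICC
- true coverage of a nominal 95% interval for bias = 2Φ(1.96/√DEFF) − 1
- width of the correct interval relative to the pooled one = √DEFF

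| m | DEFF at ICC 0.1 / 0.3 / 0.5 | Coverage |
|---|---|---|
| 3 | 1.2 / 1.6 / 2.0 | 92.6 / 87.9 / 83.4% |
| 6 | 1.5 / 2.5 / 3.5 | 89.0 / 78.5 / 70.5% |
| 17 | 2.6 / 5.8 / 9.0 | 77.6 / 58.4 / 48.6% |

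The width ratio runs from √1.2 = 1.10 to √9.0 = 3.00. The number of patients does not enter, so 50 or 60 makes no difference here.

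**3. The limits themselves.** With N region pairs, the expected pooled variance is σ²(N − DEFF)/(N − 1). In the worst row, N = 60 × 17 = 1020 and (1020 − 9)/1019 = 0.992. The SD is therefore low by only about 0.4%, and the limits stay nearly unbiased.

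**4. Can clustering arise on relative uptake?** Suppose each camera's uptake is divided by the mean of k separate reference regions, with independent errors of relative variance s² per region and camera. A difference then has variance of about 2s²(1 + 1/k), of which 2s²/k is shared across the patient. So ICC = (1/k)/(1 + 1/k) = 1/(k + 1), which is 0.10, 0.25 and 0.50 for k = 9, 3 and 1. In simulation (60 patients, 4000 replicates), coverage for k = 9/3/1 was:
- 3 regions: 92.9 / 88.7 / 84.6%
- 6 regions: 89.2 / 81.2 / 70.4%
- 17 regions: 76.9 / 61.0 / 48.4%

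Patient-level intervals covered 94.1% to 95.4%. Normalising to the hottest region gave 95.2 / 86.6 / 70.0% for 3/6/17 regions. Normalising to the mean of all regions gives a negative ICC (−0.50 / −0.20 / −0.06) and no under-coverage, but the overall bias is then zero by construction. The choice of reference therefore has to be named.

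**5. Why a region term.** Biases of +10 points in three regions and −10 in three average to 0. With a within-region SD of 10, the pooled SD becomes √(10² + 10²) = 14.1. Region means recover the ±10.

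**The case against.** The strongest reply is that Bland-Altman, the method that exposes bias, is already in the plan. The plan has no test, pass mark or agreement limit that r could corrupt, so harm from r needs a report that leads with r and disregards its own plot. Under-coverage needs two further steps, pooling and confidence intervals, and the plan states neither. The segments in section 10.2 belong to cited studies. On relative uptake, the only scale the documents specify, a uniform under-read cancels. Variance components could also be computed later from the same data.

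Most of this stands, and it limits the size of the point. A reader might infer more than the documents support:

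- *That the plan substitutes correlation for an agreement method.* It does not; both are named.
- *That it will treat regions as independent and report invalid intervals.* It neither proposes nor rules out pooling, and mentions no intervals.
- *That the main comparison has no planned analysis.* Section 17.7 appears to use cardiac MRI for the research session, so section 9.3 can be read to include PET/MR. The comparison is not clearly named, rather than shown to be absent.
- *That the plotted limits would be wrong.* Step 3 shows that they barely change.

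The reply does not remove the fact that section 9.3 calls correlation a measure of agreement, or that Aim 1's unit is unstated. Nor does the lack of an acceptance limit excuse the wording. The fix settles which statistics carry the conclusion; it sets no pass mark, since the documents give no figure for one.

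**Conclusion.** The concern holds in a limited form. Section 9.3 names a correlation coefficient as evidence of agreement, which it cannot supply. It does not clearly name the camera comparison and states no unit of analysis for regional uptake.

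The likely consequence is that r is reported as agreement. The conditional one is intervals for bias with coverage between about 93% (3 regions, ICC 0.1) and 49% (17 regions, ICC 0.5). Those figures are illustrative: region counts, ICCs, error sizes and normalisations are all assumed, and some normalisations give no loss. The r = 0.99 example applies to un-normalised uptake only. This is worth correcting before analysis, while regions and reference can be fixed without sight of the results. It is not evidence that any stated figure is wrong.

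**What to change.** Replace the sentence in section 9.3 with text by aim, along these lines:

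> Aim 1: agreement between PET/MR and clinical PET or PET/CT will be assessed on paired differences in regional FDG uptake, with the regions and any reference region named before analysis. Bland-Altman bias and 95% limits will be estimated allowing for multiple regions per patient (patient as random effect, region as fixed effect), with patient-clustered confidence intervals and a check for proportional bias. Between- and within-patient variance components will be reported for planning the larger trial. Conclusions on agreement rest on bias and limits; any correlation coefficient is descriptive only.
>
> Aim 2: Bland-Altman analysis will be used only where PET and MRI measure the same quantity in the same units (for example infarct extent).
>
> Aim 3: MRI strain and relative FDG uptake will be analysed by correlation, as association, allowing for clustering if analysed by region. No Bland-Altman analysis will be done, because these are different quantities.

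Add one caution. The research scan follows the clinical one "with no additional administration of any radiopharmaceutical", so any un-normalised PET/MR versus PET/CT difference mixes camera with later imaging time. A full un-normalised comparison backed by camera cross-calibration is more than this pilot needs.

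Aims 4 to 6 are outside this point. Because the existing sentence is replaced, the revised section should also say how they are analysed.

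The cost is analysis wording, slightly more analysis work, and intervals about 1.1 to 3 times the width of those from pooling, under the assumed range. No scans or patients are added.
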